3.2 DRUG ADMINISTRATION

- Lenalidomide 10 mg once daily, given by mouth on days 1-21, of repeated 28-day cycles, to continue until disease progression, unacceptable toxicity or completion of two years of lenalidomide therapy and the 30 day safety follow-up visit.
- Lenalidomide will be prescribed monthly by Clinical Center physicians. Upon completion of phone counseling per the REMS® program, the NIH Clinical Center physician will prescribe a 28 day supply of lenalidomide to be sent to the patient by express delivery beginning with Cycle 4.

Abbreviated Title: Revlimid maintenance for MM

Version Date: 01/06/2017

- Females of childbearing potential (FCBP) patients will be required to have pregnancy testing as outlined in Appendix B: Risks of Fetal Exposure, Pregnancy Testing Guidelines and Acceptable Birth Control Methods: Risks of Fetal Exposure, Pregnancy Testing Guidelines and Acceptable Birth Control Methods; and may have the pregnancy test performed by local treating physician. In these cases, the local physician will submit the results to NIH Clinical Center for review. Upon receipt of negative pregnancy test result and completion of phone counseling per the REMS® program, NIH Clinical physician will prescribe a 28 day supply of lenalidomide to be sent to the patient by express delivery.
- Lenalidomide capsules should be swallowed whole, and should not be broken, chewed or opened.
- If vomiting occurs within 15 minutes and the whole capsule is present in the emesis then the dose can be repeated.
- If a dose of lenalidomide is missed, it should be taken as soon as possible on the same day. If it is missed for the entire day, it should not be made up.
- Patients who take more than the prescribed dose of lenalidomide should be instructed to seek emergency medical care if needed and contact study staff immediately.
- Lenalidomide (Revlimid®) will be provided to research subjects for the duration of their participation in this trial at no charge to them or their insurance providers. Lenalidomide will be provided in accordance with the REMS® program of Celgene Corporation. Per standard REMS® requirements all physicians who prescribe lenalidomide for research subjects enrolled into this trial, and all research subjects enrolled into this trial, must be registered in and must comply with all requirements of the REMS® program. Prescriptions must be filled within 7 days for females of childbearing potential and 14 days for all other risk categories. Only enough lenalidomide for one cycle of therapy will be supplied to the patient each cycle.
- Patients should be instructed never to give lenalidomide to another person and to return any unused capsules to their research coordinator at the end of treatment.
- Patients should not donate blood during therapy and for at least 28 days following discontinuation of lenalidomide.
- Patients will be required to take oral Aspirin 81 mg or 325 mg or alternative anticoagulation therapy every day for the duration of their participation in the study.

3.3 DOSE MODIFICATIONS

Before each cycle, patients will be evaluated for possible toxicities that may have occurred after the previous dose(s). Toxicities will be assessed according to the NCI Common Terminology Criteria for Adverse Events (CTCAE) (<http://ctep.cancer.gov/reporting/ctc.html>). Each adverse event (AE) attributed to lenalidomide will be carefully recorded, so that the dose modifications can be made accordingly. If multiple toxicities are noted, the dose adjustments and/or delays will be made according to guidelines that address the most severe toxicity.

3.3.1 Dose reduction steps:

Abbreviated Title: Revlimid maintenance for MM

Version Date: 01/06/2017

Dose	Lenalidomide
Baseline dose	10 mg
One level dose reduction	5 mg
Two level dose reductions	5 mg every other day

3.3.2 Dose adjustments for Thrombocytopenia:

Thrombocytopenia	Recommended Course
First Episode- Platelet count $< 25 \times 10^9/L$	Hold lenalidomide. Hold prophylactic anti-coagulation. Monitor CBC weekly. Platelet count returns to $\geq 25 \times 10^9/L$. Resume lenalidomide at 10 mg. Resume prophylactic anti-coagulation, if no bleeding.
Subsequent Episodes- Platelet count $< 25 \times 10^9/L$	Hold lenalidomide. Hold prophylactic anti-coagulation. Monitor CBC weekly. Platelet count returns to $\geq 25 \times 10^9/L$. Resume lenalidomide at next lower dose level. Resume prophylactic anti-coagulation, if no bleeding. Do not decrease dose below 5 mg every other day.

*In case of thrombocytopenia, the decision to modify the dose of lenalidomide, administer platelet transfusions, and resume anti-coagulation may be based on the clinical judgement of the PI.

3.3.3 Dose adjustments for Neutropenia:

Neutropenia	Recommended Course
First episode- (Neutropenia is the only hematologic toxicity) ANC $< 0.5 \times 10^9/L$ (grade 4) ANC $< 1.0 \times 10^9/L$ (grade 3) with fever/sepsis	Hold lenalidomide. Consider growth factors. Monitor CBC weekly. ANC returns to $\geq 0.5 \times 10^9/L$, and fever/sepsis have resolved. Resume lenalidomide at same dose level, and consider stopping growth factors.
First episode- (Hematologic toxicities other than neutropenia are observed) ANC $< 0.5 \times 10^9/L$ (grade 4) ANC $< 1.0 \times 10^9/L$ (grade 3) with fever/ sepsis	Hold lenalidomide. Consider growth factors. Monitor CBC weekly. ANC returns to $\geq 0.5 \times 10^9/L$, other toxicities and fever/sepsis have resolved. Resume lenalidomide at next lower dose level, and consider stopping growth factors.

Abbreviated Title: Revlimid maintenance for MM

Version Date: 01/06/2017

Subsequent Episodes-	Hold lenalidomide. Add growth factors.
ANC < 0.5 x 10 ⁹ /L (grade 4)	Monitor CBC weekly.
ANC < 1.0 x 10 ⁹ /L (grade 3) with fever/sepsis	ANC returns to ≥ 0.5 x 10 ⁹ /L, and fever/sepsis have resolved. Resume lenalidomide at next lower dose level and consider stopping growth factors. Do not decrease dose below 5 mg every other day.

*Fever defined as single temperature of 38.3°C or sustained temperature of 38°C for > 1 hour. In case of neutropenia, the decision to start/continue growth factors (such as filgrastim, pegfilgrastim), and/or reduce the dose of lenalidomide may be based on the clinical judgment of the PI.

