3.3.4 Dose adjustments for Non hematologic toxicity

Lenalidomide Common Non-hematologic Toxicities	Dose Modifications
Non Blistering Rash	If Grade 3, hold lenalidomide, and restart at next lower dose level once rash improves to ≤ Grade 2.
Blistering, exfoliative or bullous rash (any grade), or suspected Stevens Johnson Syndrome (SJS) or Toxic Epidermal Necrolysis (TEN)	Discontinue lenalidomide and remove patient from therapy.
Venous or arterial thrombosis/embolism	Hold lenalidomide and start therapeutic anticoagulation. Restart lenalidomide at investigator's discretion at current or reduced dose level. Patient should continue anticoagulation therapy during the course of lenalidomide treatment. Additional work up to determine the cause of thromboembolic events may be done as clinically indicated at the discretion of investigator.
Renal Dysfunction CrCl based on Cockcroft-Gault formula: CrCl = (140 – Age) x Mass (in kilograms) x [0.85 if Female] 72 x Serum Creatinine (in mg/dL)	
 CrCl 31-60 ml/min – no dose modifications CrCl ≤30 mL/min (not requiring dialysis) – Dose reduce Lenalidomide to 10 mg every 48 hours CrCl ≤30 mL/min (requiring dialysis) – Decrease Lenalidomide to 5 mg daily and on dialysis days, dose lenalidomide after dialysis.
Other non-hematologic grade 3/4 toxicities judged to be related to lenalidomide. Readily reversible electrolyte and metabolic abnormalities or infections controlled by appropriate therapy are exempt.	Hold treatment and restart at next lower dose level when toxicity has resolved to ≤Grade 2

3.3.5 Monitoring (see study calendar for more specific details) Please Note: Day 1 may be delayed for up to one week for Cycle 2 and beyond.

3.3.5.1 Routine labs (CBC with diff, retic count, acute care panel, mineral panel, hepatic panel, LDH, uric acid) will be performed on Day 1 (within 3 days prior) and Day 15

Abbreviated Title: Revlimid maintenance for MM

Version Date: 01/06/2017

(within 3 days prior) of first cycle, on Day 1 (within 3 days prior) of cycles 2, 4 and 7 and on Day 1 (within 3 days prior) of every third cycle starting at cycle 10 at scheduled clinic visits, at the time of documented CR, and at disease progression (see study calendar).

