3.5 CRITERIA FOR REMOVAL FROM PROTOCOL THERAPY AND OFF STUDY CRITERIA

3.5.1 Criteria for removal from protocol therapy

- 3.5.1.1 Patients with medically concerning grade 3 or 4 adverse events related to study drug may be taken off therapy at the discretion of the principal investigator.
- 3.5.1.2 Toxicity has not resolved after 8 weeks of withholding treatment
- 3.5.1.3 Grade 4 non-blistering rash, or blistering rash of any grade
- 3.5.1.4 Grade 4 neuropathy
- 3.5.1.5 Grade 4 hypersensitivity reaction
- 3.5.1.6 Progression of disease
- 3.5.1.7 Patient chooses to go off therapy
- 3.5.1.8 The principal investigator may remove patient from protocol therapy if deemed necessary due to medical conditions, compliance, etc.
- 3.5.1.9 Diagnosis of new malignancy
- 3.5.1.10 Patient becomes pregnant.

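### The Section 3.3 rule for simultaneous toxicities can restart a patient with Grade 3 rash plus first Grade 4 neutropenia at a higher dose than a patient with the rash alone

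*Combined protocol and SAP*

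**What the plan says.** Section 3.3 opens with a general rule: "If multiple toxicities are noted, the dose adjustments and/or delays will be made according to guidelines that address the most severe toxicity". The rule covers both dose and delay and selects a single guideline. The same paragraph has toxicities assessed by CTCAE. It does not define most severe further, gives no rule for ties, and does not say whether severity is judged at onset or again at restart.

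The dose table in 3.3.1 starts at 10 mg; the line "One level dose reduction" gives 5 mg.

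The rows that matter here are:
- **3.3.3, row 1** (first episode of ANC below 0.5, printed as Grade 4, with neutropenia the only hematologic toxicity): hold until ANC is at least 0.5 and fever or sepsis has resolved, then "Resume lenalidomide at same dose level, and consider stopping growth factors".
- **3.3.4, non-blistering rash:** "If Grade 3, hold lenalidomide, and restart at next lower dose level once rash improves to ≤ Grade 2".
- **3.3.4, other related Grade 3/4 non-hematologic toxicity** (with stated exemptions): "Hold treatment and restart at next lower dose level when toxicity has resolved to ≤Grade 2".

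A footnote to 3.3.3 lets the PI use clinical judgment on growth factors and on reducing the dose. Section 3.5.1.1 lets the PI take a patient off therapy for a medically concerning related Grade 3 or 4 event.

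**The concern.** A rule that follows the most severe toxicity is safe only if the higher grade always carries the stricter restart instruction. In these tables it does not. The first Grade 4 neutropenia row restarts without a dose step, whereas the Grade 3 non-hematologic rows require a dose step and recovery of that toxicity. When the two occur together, the general sentence selects the more lenient row, and nothing in that row brings back the condition attached to the other toxicity.

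What is at stake is that two clinicians could reach different restart doses and recovery conditions for the same patient, each able to point to protocol text in support.

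**Working it through.** No sample size, power or significance figure bears on this point. The check applies the Section 3.3 sentence to the rows and compares the result with the row for the second toxicity alone.

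**Inputs.** Starting dose 10 mg and first reduction 5 mg (3.3.1). Dosing days 1-21 of a 28-day cycle (3.2). Restart rows from 3.3.3 and 3.3.4 as set out above. Two assumptions: severity is ranked by CTCAE grade, and the 5 mg level keeps the 21-day schedule, which 3.3.1 does not restate.

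**Step 1: which neutropenia row applies.** Row 1 of 3.3.3 requires that neutropenia be the only hematologic toxicity. A rash is not hematologic, so a patient with first Grade 4 neutropenia and Grade 3 rash still falls in row 1. Row 2, which asks for other toxicities to have resolved and lowers the dose, applies only if another hematologic toxicity is present.

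**Step 2: which guideline the 3.3 sentence selects.** Grade 4 (printed for ANC below 0.5) outranks Grade 3 (printed for the rash), so the neutropenia row governs both dose and delay.

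**Step 3: compare.**

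| Patient on 10 mg | Governing row | Restart dose | Restart condition | Per cycle |
|---|---|---|---|---|
| Grade 3 rash alone | 3.3.4 rash row | 5 mg | Rash at Grade 2 or less | 5 × 21 = 105 mg |
| Same rash plus first isolated Grade 4 neutropenia | 3.3.3 row 1, through 3.3 | 10 mg | ANC at least 0.5, fever or sepsis resolved; nothing on rash | 10 × 21 = 210 mg |

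Ratio of restart doses: 10 / 5 = 2.

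Replacing the rash with another related Grade 3 non-hematologic toxicity that is not exempt gives the same comparison, because that row also requires the next lower level and recovery to Grade 2 or less.

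**Step 4: timing.** The second patient restarts earlier only if two things hold: ANC recovers before the rash does, and severity is not judged again at restart. If it is judged again once ANC has recovered, the persisting Grade 3 rash may then be the most severe toxicity, and its own row would apply. The text does not settle this.

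**The case against.** The strongest reply is that a 10 mg restart with active Grade 3 rash is not an order. The course in 3.3.3 is headed as recommended, its footnote lets the PI reduce the dose, 3.5.1.1 allows removal, and 11.1.2 says interruption or discontinuation should be considered for Grade 2-3 rash. Also, most severe is not expressly defined as highest grade. All of this is true, and it limits the practical risk. It does not remove the conflict: these provisions permit a different course without requiring one, and no other scale for severity is named.

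A reader might also infer stronger points, which the documents do not support:
- **That the 3.3 sentence cancels removal for blistering rash.** It governs dose adjustments and delays. Removal stands separately in 3.3.4 and in 3.5.1.3 ("Grade 4 non-blistering rash, or blistering rash of any grade").
- **That a first platelet count below 25 gives the same result.** Row 1 of 3.3.2 does say "Resume lenalidomide at 10 mg", but no grade is printed for that count, so the protocol alone does not rank it above a Grade 3 toxicity.
- **That 3.3 contradicts row 2 of 3.3.3.** When Grade 4 neutropenia occurs with another, less severe hematologic toxicity, the sentence leads to row 2, and the two agree.
- **That such pairs are common.** The list of reactions above 20% in 11.1.2 gives neither grades nor pairs.
- **That the after-cycle-3 cell counts are affected.** Neither the frequency in cycles 1-3 nor any effect on the paired comparison can be shown from the documents.

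**Conclusion.** The point holds in a narrow form. Read by CTCAE grade, the Section 3.3 sentence and the tables in 3.3.3 and 3.3.4 give different restart doses (10 mg against 5 mg, a factor of two) and different recovery conditions for a patient on 10 mg who has a first, isolated Grade 4 neutropenia together with a Grade 3 non-blistering rash or another related, non-exempt Grade 3 non-hematologic toxicity. An earlier restart is possible but not established.

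The conclusion rests on ranking severity by grade. It does not extend to every pair of toxicities, because the paradox arises only where the more severe toxicity has the more lenient row. It is nevertheless a conflict between a stated rule and the tables it governs, not merely a missing detail, and it should be corrected.

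**What to change.** Reconcile the sentence in 3.3 with 3.3.3 and 3.3.4. For a cytopenia and a non-hematologic toxicity that occur together and whose rows differ, the text should:
- give one instruction covering both the restart level and the recovery condition;
- state how most severe is judged, including ties;
- state when it is judged: at onset, at restart, or both.

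Which instruction governs is for the clinical leads to decide; this review does not propose one. The cost is one or two sentences in an amendment, with no extra visits, tests or patients.

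### Two dose rules need correcting: the first platelet episode resumes at a fixed 10 mg whatever the current dose, and the generic grade 3/4 row restarts lenalidomide after angioedema, which section 11.1.2 rules out

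*Combined protocol and SAP*

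**What the plan says.** **Dose ladder and platelets.** Section 3.3.1 sets a baseline of 10 mg, a first reduction to 5 mg and a second to "5 mg every other day". In section 3.3.2, a first platelet count below 25 x 10^9/L leads to a hold with weekly blood counts and, on recovery to at least 25, "Resume lenalidomide at 10 mg". Later episodes step the dose down. The column presents these as recommendations, and a footnote adds that "the decision to modify the dose of lenalidomide, administer platelet transfusions, and resume anti-coagulation may be based on the clinical judgement of the PI".

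**Neutropenia.** Section 3.3.3 uses relative wording. For a first episode with no other hematologic toxicity it says "Resume lenalidomide at same dose level". For a first episode with other hematologic toxicities, and for later episodes, it says "Resume lenalidomide at next lower dose level".

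**Non-hematologic toxicity.** In section 3.3.4, grade 3 non-blistering rash means "hold lenalidomide, and restart at next lower dose level once rash improves". For blistering, exfoliative or bullous rash, or suspected SJS or TEN, the action is "Discontinue lenalidomide and remove patient from therapy". The last row covers "Other non-hematologic grade 3/4 toxicities judged to be related to lenalidomide", and its action is to hold and then restart one level lower once the event is grade 2 or less. Angioedema is not named in the table.

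**Pharmaceutical section.** Section 11.1.2 (Allergic Reactions) requires discontinuation, without resumption, for angioedema, grade 4 rash, exfoliative or bullous rash, and suspected SJS or TEN. It sets no grade limit for angioedema.

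**Removal from therapy.** Section 3.5.1.3 covers grade 4 non-blistering rash and blistering rash of any grade. Section 3.5.1.5 covers grade 4 hypersensitivity. Sections 3.5.1.1 and 3.5.1.8 allow the principal investigator to remove a patient but do not require it.

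**The concern.** The platelet row states an absolute dose where its neighbours state a relative one. If a patient has already been stepped down for neutropenia, rash or another related toxicity, a hold for severe thrombocytopenia then ends, by default, in a higher dose than the one on which it occurred. It also undoes the reduction made for the first toxicity.

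The angioedema problem is a conflict between two sections. The table that clinicians use for dosing gives a restart, while the drug-information section forbids one. What is at stake is re-exposure to full dose after a severe platelet fall, and rechallenge after a reaction in a class that section 11.1.2 says can be fatal.

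**Working it through.** The plan states no figure to reproduce here. The check is dose arithmetic for the platelet row and a comparison of rules for angioedema.

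**1. Platelet row**

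Inputs: the ladder in 3.3.1; dosing on days 1-21 of 28 (3.2). I assume that the 21-day schedule is kept after a reduction, which 3.3.1 does not state.

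A patient can be below 10 mg before a first platelet episode through the step-down rows of 3.3.3, the grade 3 rash row, or the generic grade 3/4 row of 3.3.4. The multiple-toxicity rule in 3.3 selects the guideline for the most severe toxicity. It does not say that an earlier reduction is kept.

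| Dose when held | mg per 48 h | mg over days 1-21 |
|---|---|---|
| 10 mg daily | 20 | 21 x 10 = 210 |
| 5 mg daily | 10 | 21 x 5 = 105 |
| 5 mg alternate days | 5 | 11 x 5 = 55 (start day 1) or 10 x 5 = 50 (start day 2) |

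Ratio on resuming at 10 mg daily:

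- From 5 mg daily: 20/10 = 2.0 per 48 h; 210/105 = 2.0 per cycle.
- From 5 mg on alternate days: 20/5 = 4.0 per 48 h; 210/55 = 3.8 or 210/50 = 4.2 per cycle.

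With relative wording, the same patients resume at 105 mg, or at 50 to 55 mg, per cycle (ratio 1.0). A patient still on 10 mg resumes at 10 mg under either wording.

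**2. Angioedema**

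First, where each reaction that 11.1.2 treats as a permanent stop is also a mandatory stop in 3.3.4 or 3.5.1:

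| Reaction in 11.1.2 | Mandatory stop in 3.3.4 or 3.5.1 |
|---|---|
| Grade 4 rash | 3.5.1.3 |
| Exfoliative or bullous rash | 3.3.4 |
| Suspected SJS | 3.3.4 |
| Suspected TEN | 3.3.4 |
| Angioedema | Only if grade 4 and classed as hypersensitivity (3.5.1.5) |

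Then angioedema by grade, against 11.1.2 (stop, do not resume):

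- Grade 1-2: no row of 3.3.4 applies, so 11.1.2 is the only rule. No conflict.
- Grade 3, related: the generic row restarts one level lower. **Conflict.** 3.5.1.5 does not reach grade 3; 3.5.1.1 and 3.5.1.8 are discretionary.
- Grade 4, classed as hypersensitivity: 3.5.1.5 removes the patient. This agrees with 11.1.2.
- Grade 4, related, not so classed: generic row. **Conflict.**

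The generic row's exemptions (readily reversible electrolyte and metabolic abnormalities, controlled infections) do not cover angioedema.

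**The case against.** **Platelets.** The first-episode row was probably written for a patient still on 10 mg. Section 3.3.1 describes reductions only, the table is a recommendation, and the footnote gives the principal investigator discretion over exactly this decision. Treatment resumes only after a hold, weekly counts and recovery to at least 25. The scenario needs an earlier reduction for something else, and the 4-fold figure needs two. All of this stands, and it limits how often the row could mislead. It does not correct the row. The discretion is permissive and leaves 10 mg as the default, and 3.3.3 has a similar footnote yet still states a relative rule.

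**Angioedema.** The stop is already in the protocol, and a rule that names a reaction should prevail over a catch-all row. Prescribing is by Clinical Center physicians, the team discusses each patient regularly (7.3.1), and 2.1.2.20 excludes patients with earlier severe events or hypersensitivity to thalidomide or lenalidomide. A careful investigator would therefore probably stop. However, 3.3.4 does not refer to 11.1.2, nothing says which section governs, and 2.1.2.20 does not address a first reaction on study. It could also be said that the table is headed as covering common toxicities. It nevertheless names SJS and TEN, which are not in the 11.1.2 list of common reactions, and its last row takes in all other related grade 3/4 events.

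**Stronger readings that the documents do not support.** A reader might infer that grade 1-2 angioedema is also contradicted or left uncovered. It is not: 11.1.2 alone applies, and it says to stop. A reader might also infer that the two rows for creatinine clearance of 30 mL/min or less raise the dose of a patient on 5 mg alternate days, because their fixed doses come to 10 mg per 48 h against 5 mg. Both rows are worded as reductions, which excludes an increase. Designing a further dose step below them would be a new dosing choice, not the correction of an error.

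**Conclusion.** Both points hold and should be fixed on patient-safety grounds. The platelet row, as a default subject to the principal investigator's judgement, returns an already reduced patient to full dose: 2-fold from 5 mg daily, about 4-fold (3.8 to 4.2 per cycle) from 5 mg on alternate days. It would be too strong to say that the protocol obliges re-escalation. For related grade 3 angioedema, and for grade 4 not classed as hypersensitivity, 3.3.4 and 11.1.2 give opposite instructions. This is the firmer of the two points, because it is a contradiction in the text and not an unstated condition.

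The ratios are dose ratios, not measures of risk, and the cycle figures assume that the 21-day schedule is kept. The documents give no rate from which to count affected patients; probably few of the planned 28. The primary comparison, its sample size and its power are unaffected.

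**What to change.** - **3.3.2, first episode:** replace the fixed 10 mg with resumption at the same dose level, matching the first-episode neutropenia row. Nothing changes for patients still on 10 mg.
- **3.3.4:** add angioedema of any grade to the existing discontinue row, stating that lenalidomide is not resumed. This matches 11.1.2, which sets no grade limit.
- **3.5.1:** add angioedema as a mandatory reason for removal from protocol therapy.

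The cost is a few words in one cell, one term in an existing row and one list item. No visits, procedures or patients are added, and the statistical section stays as it is.
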